This study proposes to recruit a relatively young (ages 13-17) sample. If the researchers have reasonable cause to believe that child abuse or neglect is occurring, or there are circumstances which might result in child abuse or neglect, they will comply with California state laws by filing a child abuse report with the Department of Child and Family Services. If the research staff believe that a participant is at risk of harming someone else, they are required to take necessary actions. These actions include notifying the parent of the participant's intentions, notifying others who might be affected (i.e., intended victims), or notifying the police or the Department of Child Services. In these cases, the research staff will be unable to preserve the participant's confidentiality. These limits to confidentiality will be spelled out in the participants' consent and assent forms. We will notify parents if we learn that an adolescent participant is actively abusing alcohol or drugs in a way that is life-threatening or otherwise a danger to him- or herself or others. If an adolescent participant has experimented with a drug or alcohol on a single occasion, notifying the parents may not be indicated. Nonetheless, it will be necessary to monitor this behavior in family or individual support sessions. If we disclose these behaviors to parents, we will meet with the family to help resolve family conflicts and introduce preventative measures. Additional counseling sessions beyond the required number will be tabulated and included as covariates in the treatment/outcome analyses.

Protections Against Risk

Data safety will be maintained to the most rigorous standards as detailed above. Survey responses will be entered into Chorus. Electronic and audio data will be stored within the UCLA Health System's encrypted firewall, will be password protected, and protected by anti-virus software. Any hard copies of participants' data will only contain a unique study ID and stored in a locked filing cabinet within the PI's office. All study codes (including a link between participant names and identifying information) will be kept in a password-protected electronic file on a secure server. Password access will be limited to the PI and to any individuals that are IRB

approved for this study. All study links between participant IDs, names, and identifying information will be destroyed when the study has ended. Approval of all study documents will go through UCLA's IRB.

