Participants may require out-of-protocol emergency services such as hospitalization or other psychosocial programs. These participants will be retained in the protocol whenever possible. A participant who needs to be hospitalized (e.g., for suicidality) will be reentered into the protocol after hospital discharge if the participant and family agree to continue. Participants will not be withdrawn if they seek ancillary psychosocial treatments outside of the study. We recognize that the availability of adjunctive non-protocol treatments could statistically confound our results, especially if they occur in one treatment condition more than another. This potential threat to internal validity must be balanced against the clinical needs of the adolescent participant, which may not be met by study protocol interventions. As indicated, we will record each participant's non-protocol treatments (e.g., medications received, frequency and type of extra psychotherapy sessions) using a *Treatment Utilization Form*. We will examine in the data analyses whether the adolescents in the two treatment conditions differ in the intensity (e.g., number of non-protocol sessions), costs, or duration of ancillary services or crisis sessions. We will then use these variables as covariates when evaluating the effects of treatment condition on the teen's symptomatic, functional, or family outcome variables. In the primary mentor's prior studies in mood disorders (e.g., [name] et al., 2013), youth at high-risk for bipolar disorder in FFT and Enhanced Care did not differ on the frequency of variables such as undertaking ancillary therapies, emergency room visits, school counseling, or hospitalizations.

Circumstances That May Require Study Withdrawal

Noncompliance. Participants will be withdrawn from the protocol if they are noncompliant with the study procedures (for example, miss 4 consecutive treatment sessions without calling ahead; refuse to participate in follow-up interviews). The circumstances that may require administrative withdrawal will be spelled out in the consent forms.

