The power calculation assumes a two-sided significance level, $\alpha=.05$, and a within-subject correlation of $r=.5$ between repeated measures. Under these calculations, for outcomes measures at the three primary assessment time-points, we have 80% power to detect an overall group by time interaction corresponding to a differential treatment effect across the two study arms with an effect size of $f=.30$, just above the above Cohen's threshold for a medium effect ($f=.25$). Thus, recruiting 60 participants will provide ample data for this pilot RCT in order for us to determine initial clinical meaningfulness for the larger grant application to follow this study. However, in accordance with NIMH guidance on the role of pilot RCTs (see: <https://grants.nih.gov/grants/guide/rfa-files/RFA-MH-18-706.html>), this study does not propose to formally assess clinical efficacy or estimates of effect size, due to the unreliability of estimates and limited statistical power yielded from pilot studies.

Statistical analyses

Aim 1 – App acceptability:

- Open trial acceptability: Following the open-trial, we will score participants' rating of app acceptability and treatment satisfaction and burden. We expect high ratings of acceptability (scores>4/5) for the treatment and the app. We will also calculate participant adherence via the extent of weekly practice and percentage of weekly skills practiced. We expect the percentage of weekly skills practiced to be greater than our pilot study as well as the average homework adherence in the literature (>50%).

Aim 2 – Pilot RCT of App-UP:

- Primary Analyses: Treatment conditions will be compared using a general linear mixed modeling (GLMM) approach for the weekly measurements of treatment adherence (both self-report and clinician rated measures) using IBM SPSS software. Time will be based on the standard interval assessments of the study – the baseline, post-treatment, and follow-up assessment). Time, treatment condition, and their interaction will be the primary predictors (controlling for any significant covariates).

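### Significance in the trial's own data decides which covariates enter the mixed models, and the only covariates named elsewhere are post-randomisation; a small fixed baseline set is better

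*Combined protocol and SAP*

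**What the plan says.** Statistical analyses, Aim 2, Primary Analyses: adherence is compared between arms in a mixed model. "Time, treatment condition, and their interaction will be the primary predictors", with the parenthesis "controlling for any significant covariates". The Secondary analyses paragraph repeats both for psychiatric symptoms, psychosocial functioning and emotion regulation. The one-way ANOVAs for the measures collected at post-treatment carry no covariate rule.

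No baseline covariate or stratification factor is named anywhere. Two sections outside the statistical part do name covariates:

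- Limits to Confidentiality: "Additional counseling sessions beyond the required number will be tabulated and included as covariates in the treatment/outcome analyses".
- Availability of Other Ancillary Treatments: intensity, cost and duration of ancillary or crisis services are first compared between arms. Then "We will then use these variables as covariates when evaluating the effects of treatment condition", here for symptomatic, functional and family outcomes.

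Power calculations sets a two-sided .05 level and states "we have 80% power to detect an overall group by time interaction" at f = .30. It mentions no covariates.

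**The concern.** The parenthesis is a selection rule, so this is more than a missing list. The p-values of 50 to 60 participants decide the model, and treatment is then tested as if that model had been fixed in advance. 'Significant' has at least three natural meanings: significant in the full model, associated with the outcome one at a time, or different between arms. These have different consequences, and the choice can be made after the results are seen.

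The covariates named elsewhere raise a further problem. Treatment can change how much extra counseling or crisis care a participant uses, so adjusting for it can remove part of a real effect or create a spurious one.

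At stake is the treatment comparison that is meant to inform the larger grant application.

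**Working it through.** **Inputs from the plan.** 60 randomised 1:1; 15-20% dropout, so 60 × 0.85 = 51 to 60 × 0.80 = 48, which the plan rounds to about 50 (25 per arm); three time points; within-subject r = .5; two-sided .05.

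**Assumptions, not in the plan.** 5 to 20 independent candidate covariates, one or two of them prognostic (r = .3 or .5, or joint R² of 0.3 or 0.5). Power is evaluated at d = 2f = 0.6.

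**The plan's own figure.** The stated 80% for the interaction was not reproduced. By noncentral F at N = 50, the conventions tried give 99.8% (standard within-between formula using r = .5), 91.0% (r ignored), 75.7% (Cohen) and 73.8% (SPSS-type f). At N = 60 they give more than 99.9%, 95.4%, 83.6% and 82.2%. The between-subject group test at N = 60 gives 79.9%, but that is not the test described. This is a separate matter, and nothing below depends on it.

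**Step 1: closed-form checks, 25 per arm, outcome SD 1.**

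- Unadjusted SE = √(2/25) = 0.283.
- SE with a fixed covariate of r = .5 = 0.283 × √(1 − 0.25) = 0.245.
- Chance that a covariate with true r = .3 misses p < .05 in a univariate test: Fisher z = 0.3095 × √47 = 2.12, so Φ(1.96 − 2.12) ≈ 0.44. Simulation gives 42-43%.

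**Step 2: simulation of the treatment main effect under no effect (nominal 5%).**

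| Meaning of 'significant' | Type I error | Other result |
|---|---|---|
| Significant in full model, then refit | 5.3-6.3% (5 or 10 candidates); about 6% (8); about 7% (20) | power about equal to the fixed pair |
| Univariate association with outcome | 4.3-5.3% | r = .3 covariate dropped in 42-43% of trials |
| Different between arms | 3.2-4.0% when covariates are prognostic (5 or 10 candidates) | SE 0.287 against 0.247 when fixed (r = .5, 8 candidates) |
| Meaning chosen after seeing results | 5.8-9.3% | – |
| Fixed prognostic pair | 4.2-5.1% | – |

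The between-arm rule widens the SE by 0.287/0.247 − 1 = 16%.

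Power at d = 0.6 (R² = 0.3 / 0.5):

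- unadjusted: 54-55% in both cases;
- between-arm selection: 54% / 53%;
- univariate selection: 64-65% / 78-79%;
- full-model selection: 68-69% / 81%;
- fixed prognostic pair: 68-69% / 81-82%;
- fixed set of ten, eight of them noise: 60% / 74%, which is why the set should be small.

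**Step 3: the interaction.** Three time points, 25 per arm, random intercept, time-invariant covariate entered as a main effect. In one simulated complete data set the two group-by-time estimates were 0.0011 and −0.0536 with or without the covariate, both with SE 0.2851. The SE of the group term fell from 0.296 to 0.245. With 17% dropout the interaction estimates were 0.2423 and 0.0427 without the covariate and 0.2423 and 0.0254 with it. Their SEs changed by no more than 0.001.

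**Step 4: adjusting for a post-randomisation covariate.** Treatment has no effect on the outcome but shifts the covariate, which is correlated with the outcome.

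- Shift 0: bias −0.003, type I error 5.4%.
- Shift 0.3 SD: bias 0.108 SD, type I error 6.7%.
- Shift 0.5 SD: bias 0.184 SD, type I error 9.9%.

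Bias is the shift times the within-arm slope of outcome on covariate. These runs imply a slope of about 0.36-0.37 (0.108/0.3 and 0.184/0.5). Both the shift and the slope are assumptions.

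**The case against.** The strongest objection is that the plan powers the group-by-time interaction, while the selection results above concern a single treatment effect. Step 3 bears this out. A reader might infer that the interaction result depends on which covariates cross .05. For time-invariant main-effect covariates and complete data it does not, and with moderate dropout it barely moves. The same holds for a post-randomisation count entered as one total per participant. What remains is the treatment main effect, covariate-by-time terms and time-varying covariates. The main effect still matters: treatment is itself listed among the primary predictors, and adherence to the study treatment has no obvious pre-treatment value from which to measure change.

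A reader might also infer that the 5% level fails in general. It does not: univariate selection shows no inflation, and between-arm selection is conservative. The figure of about 7% needs 20 candidates, a number that the plan does not give. Nor does every reading lose power, since full-model selection matches the fixed pair.

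A third tempting inference is that adding the baseline score as a covariate would by itself bring the precision gain. In the secondary models baseline is already one of the outcome time points. Adding it again puts it on both sides of the model, and in a check of 40 simulated trials the SE of the post-treatment interaction stayed at 0.277.

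Finally, the plan says that this pilot does not propose to assess efficacy formally. That lowers the stakes. It does not remove them, because the model-based comparisons are still planned and are meant to support the next application.

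**Conclusion.** The point holds in a limited form. Covariates enter on significance in the trial's own data, and the only ones named elsewhere are post-randomisation.

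For the treatment main effect, the consequence is one of three: modest inflation (about 6% with 8 candidates, about 7% with 20, full-model selection); lost precision (SE about 0.29 against 0.25 SD, between-arm selection with an r = .5 covariate left out); or little harm to the error rate (univariate selection). Leaving the meaning open until results are seen gave 5.8-9.3%. Adjusting for a covariate that treatment shifts by 0.3-0.5 SD gave a bias of 0.11-0.18 SD.

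All these figures rest on assumed numbers and strengths of covariates. The documents do not support a claim that the powered interaction is distorted by time-invariant main-effect covariates, or that the nominal level fails on every reading. The change is worth making because it is cheap and removes the ambiguity.

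**What to change.** 1. In both the primary and the secondary paragraph, replace the parenthesis with a small fixed set of baseline covariates kept whatever their p-values, for example age, baseline medication use and recruitment wave. Wave should mean the pair of groups filled together; an indicator for the single therapy group would be confounded with arm.
2. State how the baseline outcome is used, once only: either as a time point in the response, or removed from the response and used as a covariate. Where adherence has no baseline value, say so.
3. Amend Limits to Confidentiality and Availability of Other Ancillary Treatments so that extra sessions and ancillary services are described by arm and used as covariates only in sensitivity analyses. Do the same with any data-selected covariate.

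**Cost.** No new data are needed: age is an eligibility item, and current medications are recorded at the baseline visit. Recruitment fills two groups of more than 6, so at least 14 per wave; 60/14 ≈ 4.3, or about four waves and 3 degrees of freedom. With age (1) and medication (1) that makes 5, or 6 if the baseline outcome is also a covariate. The sensitivity analyses add a little work.

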treatment, is based on the premise that participants need to practice the skills in order to improve. Since participants commonly forget to do the skills, lose their homework assignments, or feel unmotivated to complete the skills, it challenges treatment developers to improve the current treatments and address these barriers to patient compliance. **We propose using a mobile app to improve patient compliance for youth at risk for SMD.** A mobile app can remind participants of skills they need to practice, provide the psychoeducation and skill-practice within the app, and provide contingencies that reward and increase motivation for skill-practice. Additionally, the large amounts of data that a mobile app collects allows for advanced statistical techniques, such as machine learning, to be applied. These efforts can provide a wide range of benefits to youth at risk for SMD and clinical science more broadly. Improving patient compliance can improve treatment outcomes, which reduces burdens on families who face these psychiatric challenges and society at-large who faces this emotional and financial burden. Additionally, through use of machine learning, we can better determine who will and who is benefitting from a skills-based treatment, like CBT. This prediction can help us better tailor treatment recommendations for patients and determine which patients will or will not benefit from a particular type of treatment.

STATISICAL DESIGN AND POWER

Power calculations

For this pilot RCT, we plan to randomize 60 participants to the randomized controlled-trial of the mobile-enhanced treatment. The two treatment groups will be randomized in a 1:1 ratio. Based on pilot trials of this treatment group as well as my primary mentor's ([name]) previous work with interventions for adolescents at high risk for SMI, we anticipate no more than 15-20% dropout by the end of the six-month study. Thus, we expect a final sample size of about 50 with full follow-up (25 in each treatment condition) across 3 assessment time-points (baseline, post-treatment, and three-month follow-up). Actual power will be higher as our general linear mixed modeling allows inclusion of data from subjects with partial data.

Additionally, data collected via the mobile application (app) should greatly increase the number of measurements.

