The remaining measures for treatment adherence (i.e., Homework Compliance Scale and Psychosocial Compliance Scale), as well as measures for app acceptability (i.e., Subjective App Usability Scale) and treatment acceptability (i.e., Subjective Treatment Acceptability) will be collected at the post-treatment assessment. Maintenance of treatment adherence will also be collected at the 3-month follow-up assessment. Treatments will be compared on these outcome measures using one-way analysis of variance (ANOVA).

- **Secondary analyses:** Treatment conditions will be compared using a general linear mixed modeling (GLMM) approach for secondary outcome variables (i.e., psychiatric functioning and psychosocial functioning) using IBM SPSS software. Time will be based on the standard interval assessments of the study – the baseline, post-treatment, and follow-up assessment). Time, treatment condition, and their interaction will be the primary predictors (controlling for any significant covariates). Psychiatric symptoms, psychosocial functioning, and emotion regulation (measured continuously) will be the outcome variables for these analyses.

We will also test a mediation analysis, with average participant adherence (measured throughout the study) as the mediator between treatment conditions and the secondary outcome variables. This will be done in two sets of analyses using the SPSS Process macros, which is a statistical package within SPSS that runs bootstrapped mediation analyses. First, the effect of treatment condition, mediated by average treatment adherence, on post-treatment psychiatric and psychosocial functioning will be examined. Second, the effect of treatment condition, mediated by average treatment adherence, on 3-month follow-up psychiatric and psychosocial functioning will be examined.

- **Exploratory analyses:** Two exploratory analyses will be examined. We will make use of the app's big data collection to begin to elucidate the app's effect on participant adherence and clinical outcomes.

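### Aim 2's Primary Analyses name no primary adherence measure: across five comparisons, a false finding that the app improves adherence has a chance of about 6% to 12%, against 2.5% nominal

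*Combined protocol and SAP*

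**What the plan says.** In the Statistical analyses section, under Aim 2, Primary Analyses, the plan compares treatment conditions with a mixed model "for the weekly measurements of treatment adherence (both self-report and clinician rated measures) using IBM SPSS software". Time, condition and their interaction are all listed as main predictors, and none of these terms is said to decide the comparison.

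Still under the same heading, it continues: "The remaining measures for treatment adherence (i.e., Homework Compliance Scale and Psychosocial Compliance Scale), as well as measures for app acceptability", followed by treatment acceptability, all taken at the post-treatment assessment. It then adds: "Maintenance of treatment adherence will also be collected at the 3-month follow-up assessment". The arms are compared on these measures by one-way ANOVA. The heading for secondary analyses comes only after this list.

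The plan names no lead measure, time point or model term. It gives no testing order and no adjustment for multiple tests, and it does not say what is concluded if the measures disagree. A significance level appears only under Power calculations: "The power calculation assumes a two-sided significance level, $\alpha=.05$, and a within-subject correlation of $r=.5$ between repeated measures".

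**The concern.** Better adherence is the effect the app is built to produce, so the adherence comparison carries the main conclusion of the RCT. As written, five comparisons could each support the statement that the app improves adherence: the two weekly ratings, the Homework Compliance Scale, the Psychosocial Compliance Scale and adherence at 3 months. If self-report favours the app and the clinician rating does not, nothing in the plan decides between them. An analyst following the plan could rest the conclusion on whichever measure reaches significance, and the two-sided .05 would not describe the error rate of that conclusion. The result is meant to inform a larger grant application, so an adherence finding chosen this way would carry forward.

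**Working it through.** **The plan's own figure.** The plan states no error rate for its set of primary comparisons, so on this point there is nothing of its own to reproduce. The nearby claim that "we have 80% power to detect an overall group by time interaction" at f = .30 does not enter the calculation. For the record, it was checked with the noncentral F at 50 completers, m = 3 time points and r = .5. The usual interaction formula gives λ = N·m·f²/(1−r) = 50×3×.09/.5 = 27 on 2 and 96 df, and power of 99.8%. Two conventions that leave r out, λ = f²(N−2)(m−1) = 8.64 and λ = f²N(m−1) = 9.0, give 73.8% and 75.7%. That mismatch is a separate matter.

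**Inputs**
- Adherence comparisons, from Primary Analyses: two weekly ratings + two scales + at least one at 3 months = 5.
- Treatment acceptability: one more test, making 6. App usability is left out because the comparator is group CBT without the app, so that arm may have no value to compare.
- Level per test: two-sided .05, taken from the power paragraph. The analysis section states none.
- Correlation ρ between measures: assumed, 0 to .8. The stated r = .5 is between repeated measures, not between different outcomes.
- No true effect on any measure, and all scales coded in the same direction.

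**Formulas.** A false result in favour of the app uses one tail, .025 per test. For k independent tests:

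- at least one favours the app: 1 − .975^k; for k = 5, 1 − .975^5 = .119
- at least one significant in either direction: 1 − .95^k; for k = 6, 1 − .95^6 = .265

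For equally correlated normal test statistics with c = 1.96, the one-tailed chance is 1 − ∫ [Φ((c − √ρ·u)/√(1−ρ))]^k φ(u) du. The two-sided version replaces the bracket by the probability of lying between −c and c.

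| Event | Tests | ρ = 0 | ρ = .5 | ρ = .8 | Single test |
|---|---|---|---|---|---|
| Favours app, adherence without the 3-month test | 4 | 9.6% | 7.8% | 5.7% | 2.5% |
| **Favours app, five adherence comparisons** | 5 | **11.9%** | **9.1%** | **6.4%** | 2.5% |
| Favours app, both scales repeated at 3 months | 6 | 14.1% | 10.4% | 6.9% | 2.5% |
| Any direction, five adherence comparisons plus treatment acceptability | 6 | 26.5% | 20.7% | 13.9% | 5% |

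For the five adherence comparisons, the rate is 11.9/2.5 = 4.8 times nominal at independence, 9.1/2.5 = 3.6 times at ρ = .5 and 6.4/2.5 = 2.6 times at ρ = .8.

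**The case against.** **Pilot status.** The plan disclaims formal assessment of efficacy and estimation of effect sizes, because pilot estimates are unreliable and power is limited. That reason applies to adherence as well, and full familywise control in a 60-person pilot would be heavy. This stands against a Bonferroni correction. It does not remove the point: the disclaimer does not call the adherence comparisons descriptive, and the plan labels them primary.

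**Implied order.** The weekly ratings come first and the scales are introduced as what remains, so the measures are not an undifferentiated set. But this is order of presentation, not a rule. Even on that reading two weekly measures lead, with nothing to choose between them.

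**Inferred level and unknown correlation.** Both objections stand. The .05 per test is borrowed from the power paragraph. Several measures of one construct in the same youths may well correlate above .5, which moves the figure toward the lower end.

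**A stronger reading.** A reader might infer that the chance of a false claim that the app improves adherence is 20% to 26%. The documents do not support that. The range belongs to a different event: any significant result, in either direction, among six two-sided tests at correlation 0 to .5. A result favouring the control arm cannot support the claim, and one of the six tests is acceptability, not adherence. Suppose two further tests are added to the six, because each mixed model could be read on either condition or its interaction with time. The favourable-direction rate among eight is then 18.3% at independence and 12.5% at ρ = .5, still below 20%.

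**Conclusion.** The gap is real and of moderate size. At least five adherence comparisons share the primary heading, with no lead measure and no rule for multiplicity or disagreement. The chance of a false finding for the app on at least one of them is about 12%, 9% or 6% at correlation 0, .5 or .8, against 2.5%. For any significant result among six tests including treatment acceptability it is about 26%, 21% or 14%, against 5%.

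These figures rest on a two-sided .05 per test, no true effect, equal correlations that the documents do not give, and each test being a single directed arm contrast. A group-by-time interaction over three time points has no single direction, which is a further reason for the plan to say which contrast it means.

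**What to change.** Name one primary adherence measure that is collected in both RCT arms, and one treatment contrast, tested once at two-sided .05. One of the weekly ratings already planned for the mixed model would serve. The text should:

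- name the instrument, which the plan does not do for either weekly rating;
- confirm that the control arm supplies it in the same way, since the Data Monitoring section describes self-report as collected on the app;
- say which model term and time window form the contrast, since the plan pairs weekly ratings with a time variable based on the three assessments;
- label the other adherence and acceptability comparisons supportive, reported as arm differences with 95% confidence intervals;
- state that the adherence conclusion rests on the primary measure.

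The percentage of weekly skills practised is a tempting choice, but the plan describes it only for the Aim 1 open trial. It should not be used unless the RCT collects it in both arms.

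The false-positive chance then returns to 5%, or 2.5% in favour of the app. The change is to wording and adds no participants. It would also help settle which adherence measure the mediation analysis averages. The cost is that a favourable result on a supportive scale alone can no longer be presented as the primary finding.

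The alternative, Bonferroni over the five adherence comparisons, uses .05/5 = .01 per test. In a two-arm ANOVA with 50 completers, it raises the standardized difference detectable with 80% power from 0.81 to 1.00. Naming one measure avoids that loss.
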